15.2 Control Group

15.2.1 Participants who make an intake appointment within one week after baseline

A TWGHs nurse will message the participants within one week after baseline reminding them to attend the intake session. Meanwhile, the nurse may contact some participants via phone for provision of further counselling or encouragement if necessary.

15.2.2 Participants who make an intake appointment more than one week after baseline

The research assistant will contact the participants around one week after baseline. The participants will receive motivational messages to encourage them to quit. They will also

be asked if they need to contact the TWGHs counsellors for early cessation support. The participants will receive reminder message from the TWGHs nurse before their intake appointment.

15.2.3 Participants who do not make an intake appointment

The participants will receive motivational messages from the research assistant around one week after baseline to encourage them to quit and enroll in one of the SC clinics.

16. Indicators and targets

Our targets will be as follows:

1. Train 40 tertiary students to be SCAs
2. Deliver brief SC advice to 2,400 smokers (1,200 in the experimental and 1,200 in the control group)

Experimental group

3. Provide NRT sample to 720 smokers (60% of all the approached smokers), who also consent to the follow-up
4. Motivate 288 smokers (40%) to use any SC services
5. Motivate 144 smokers (20%) to attempt quitting (intended abstinence for at least 24 hours).

Control group

6. 360 smokers (30% of all the approached smokers) will consent to the follow-up.
7. Motivate 72 smokers (20%) to use any SC services
8. Motivate 28 smokers (8%) smokers to attempt quitting

Both groups

9. 108 smokers report abstinence (for the past 7 days) at 6-month follow-up (30% of all

the 360 smokers who use any SC services)

17. Sample size determination

To detect a significant difference of the rate of quit attempt (20% versus 8%) with normal test and a power of 95% and 5% significance level, we need 485 subjects in the RCT (allocation ratio 2:1; 323 vs 162). Based on the method of Eldridge et al. (2006) [26], conservatively assuming that we could recruit 8 participants per session on average and the intra-cluster correlation coefficient was 0.1, the design effect is estimated to be 1.7. Thus, the minimum sample size required for the trial is 825 (=1.7 X 485) participants and 60 sessions in total. With the similar calculation, the required sample size for detecting a significant difference in the proportion of using any SC service is 421. Therefore, our targeted sample size is sufficient to answer the research question.

18. Data analyses

To assess the change of knowledge, attitude and practice of SC due to the participation of the SCA workshop, all the outcomes will be tested by McNemar's test (binary outcomes) and pair-sample t-test (continuous outcomes).

To assess the effect of NRT sampling to the recruitment outcomes, the number of smokers who accept the brief advice or consent for the trial in each promotion session will be the outcome variables of Poisson regression model, with group allocation as the predictor, and total number of approached smokers in that promotion session as the offset variable.

To compare the two primary quitting outcomes (binary) between experimental and control group, generalized estimating equations model will be used. Other secondary outcomes will be analyzed with either generalized estimating equations models (binary outcomes; e.g. tobacco abstinence) or linear mixed model (continuous outcomes; e.g. perceived importance to quit smoking).

Cost analysis will be conducted to assess if the intervention is cost-effective, as what we did in our published paper [5]. Direct operating costs included salary (of training personnel, research assistants and SCAs), recruitment, telephone follow-up and publicity items. The total operation costs for the experimental group will include the cost for NRT sampling. Costs for study design, venues for training (provided by HKU), analysis, report writing and

irrelevant administration were excluded. In each group, the cost per successfully recruiting a smoker to receive any SC service was calculated by dividing the total cost by the number of smokers who report use of any smoking cessation. Similarly, the costs per quit attempt will also be calculated.

19. Time-line:

	2018						2019												2020						
	7	8	9	10	11	12	1	2	3	4	5	6	7	8	9	10	11	12	1	2	3	4	5	6	
HCPS – NRT sampling																									
Development of the intervention, instruments and protocol																									
Site selection																									
Recruitment of ambassadors																									
Training for staff, ambassadors and nurses																									
Subject recruitments																									
3-day / 1-month follow-up																									
3-month follow-up																									
6-month follow-up (+validation)																									
6-month follow-up for SCAs																									
Data entry and cleaning																									
Data analysis																									
Report preparation																									

20. Describe any unusual or discomforting procedures to be used: Nil.

21. Are there any hazards associated with the investigation? No.

22. Ethical and legal issues

According to the Drug Database of the Drug Office under Department of Health (http://www.drugoffice.gov.hk/eps/do/en/consumer/search_drug_database.html), all NRT products (in all forms and dosages) are classified as Part 2 Poisons and are referred as over-the-counter medicines. All Part 2 Poisons are regulated by the Pharmacy and Poisons Ordinance (Cap. 138). Accordingly, Part 2 Poisons can be sold in a pharmacy (ASP) or a medicine (LSP). They can also be supplied for the purpose of medical treatment by a person, who is not necessarily a medical practitioner, who practices medicine in a clinic registered in the Medical Clinics Ordinance.

The present proposal targets to deliver a 1-week of free NRT to the smokers at the outdoor smoking hotspots, so that the smokers can obtain and use them as soon as being motivated to quit. To fully comply with the Ordinance, our collaborator (Tung Wah Group of Hospitals) has already registered a license from the Pharmacy and Poisons Board for their smoking cessation truck, which can park nearby the outdoor hotspots, so that our registered nurses can legitimately prescribe NRT to the recently-recruited smokers in this truck. The truck is a mobile clinic which can provide brief counseling sessions and medications like a clinic. The student ambassadors will mainly be responsible to approach the smokers at the hotspots and invite them to receive advice and NRT in the truck.

Other measures will also be undertaken to protect the participants: (1) Our intervention will include a brief advice about how to correctly use the NRT, side effects and other safety measures. Hence, our intervention is even safer than smokers buying over-the-counter NRT from pharmacy without any advice. (2) Only registered nurses will be responsible to provide NRT to the participants. (3) All on-site documentations will be locked in a cabinet of the truck, and handled carefully by the project coordinators. We will strictly follow the data security guideline under the University of Hong Kong. (4)

Participants who do not meet the inclusion criteria will be suggested to meet the physicians in the smoking cessation clinics and obtain the medication advice from the physicians before using NRT. They will not be included in this trial. This will help ineligible participants to use NRT safely. (5) The pilot study of the present proposal was fully reviewed and approved by the Institutional Review Board (IRB) of the University of Hong Kong / Hospital Authority Hong Kong West Cluster (Ref: UW 15-232). Therefore, our procedures and interventions met the ethical requirement and protect participants' privacy. We have already submitted the IRB application for the present study. The recruitment will only start when the research is approved by the IRB.

23. Direct access to source data/documents

The raw data will be stored in the CD-ROM and locked in a cupboard with keys kept by the Principal Investigator. Only the Investigators and Research Assistant of the project will be permitted to access to raw data and/or study record. The data will be kept for 10 years or longer after the study completed.

24. Dissemination of study result

The research findings will be disseminated through publication in international peer reviewed journals including American Journal of Health Promotion and Nicotine & Tobacco Research. Papers will also be presented in international conferences such as (1) the Annual Scientific Meeting of the Society on Research on Nicotine and Tobacco (SRNT); national conferences such as (2) the Asia Pacific Conference on Tobacco or Health and Cross-strait Conference on Tobacco Control (China, Hong Kong, Macau and Taiwan); and (3) regional conferences in Mainland China and Hong Kong.

25. Consent

Eligible participants will be invited to participate in the study by obtaining written consent.

26. Conflict of interest: None

27. Financing and insurance

This research is funded by Health and Medical Research Fund of the Food and Health Bureau.

28. References

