quitting, a multi-site cluster RCT (allocation ratio 2:1) will be used. All promotion sessions will be randomly allocated to either the experimental or the control group. The experimental group will receive medication counselling and NRT samples, while the control group only receive the advice to use NRT. Because smokers who receive NRT sampling will be more likely to participate in the study, the experimental sessions will then recruit more smokers than the control sessions. Hence, the allocation ratio of participants is arbitrarily set at 2:1. To increase comparability between the two groups, the promotion sessions of one hotspot will be randomly allocated to either group. All recruitment and quitting outcomes in the smokers between the experimental and control group will be compared.

9. Subjects

Smokers with the following inclusion criteria will be invited to participate in our RCT: (1) Hong Kong residents, (2) aged 18 to 65 years, (3) have used any tobacco products in the past month, (4) able to read and speak Chinese, (5) have not used NRT for the past month, (6) no severe angina, serious cardiac arrhythmias and hypertension, (7) have not suffered acute myocardial event in the past 4 weeks, (8) neither pregnant nor breastfeeding, (9) not under medication and treatment due to mental illness. To confirm the smoking status, in those who use conventional cigarettes, smokers' exhaled carbon monoxide will be measured on-site. Nurses on truck will measure the blood pressure if smoker is aged over 50 years old, obese by observation, or upon patient requests.

10. Procedures

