In the control sessions, all the above procedures for the experimental group will be applied, except that they will not receive an NRT sample and an instruction card about the use of NRT. Instead, they will be advised to obtain free NRT by enrolling in the SC clinics. Both groups will receive a one-page leaflet provided by the SC clinics.

As this trial is a pragmatic trial, flexible procedures will be adopted based on the actual interaction with the participant. Firstly, the intervention components and filling in of baseline questionnaire may be carried out prior to seeking the consent from the participant if it is deemed more suitable in the situation and can make the procedures run more smoothly. Secondly, if the recruitment venue is not suitable for drug dispensing, the NRT sample and the use instructions will be register-mailed to the participants' address instead of given immediately. All NRT will be prescribed by registered nurses. The research assistant will also contact the participants to confirm that they have received the NRT. This arrangement of mailing the NRT sample complies with the Pharmacy and Poisons Ordinance of the Drug Office.

12. Randomization

We will use cluster randomization based on promotion session as the cluster unit because the procedures of individual randomization are difficult in outdoor areas as found in our pilot RCT. The PI will randomly allocate the promotion sessions within a hotspot to the 2 groups by a list of group allocation which is based on a list of random numbers from Excel programme. Each hotspot will have 2 or more promotion sessions, and each session will last for about 3-4 hours. If a hotspot has 2 promotion sessions on 1 single day, the 2 sessions will be allocated into the same RCT group, and we will organize 2 more promotion sessions in this hotspot on another day.

13. Allocation concealment

All recruitment staff will know the group allocation before each promotion session, so no group concealment can be done.

14. Blinding

Participants cannot and will not be blinded to the intervention. Assessors of the follow-up outcomes and the research analysts will not be involved in the recruitment and intervention delivery, and will be blinded to the group allocation (single blindness).

15. Follow-up

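### Section 17's 8 participants per session, 825 participants and 60 sessions cannot all hold, and 60 sessions do not give the stated 95% power

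*Combined protocol and SAP*

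**What the plan says.** Section 12 makes the promotion session the cluster: "We will use cluster randomization based on promotion session as the cluster unit".

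Section 17 starts from quit-attempt rates of 20% against 8%, 95% power, 5% significance and 2:1 allocation, which gives 485 participants (323 and 162). It then inflates for clustering, "conservatively assuming that we could recruit 8 participants per session on average and the intra-cluster correlation coefficient was 0.1", to reach a design effect of 1.7. The result is that "the minimum sample size required for the trial is 825 (=1.7 X 485) participants and 60 sessions in total". After a second calculation for use of smoking cessation services, it closes: "Therefore, our targeted sample size is sufficient to answer the research question".

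Two other sections bear on the session count without stating one. Section 8 says "the allocation ratio of participants is arbitrarily set at 2:1", because experimental sessions are expected to recruit more smokers. Section 16 plans for 1,200 smokers advised in each arm, with 60% and 30% consenting to follow-up. That makes 720 and 360, or 1,080 in all. No section gives another total number of sessions, or the number per arm.

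**The concern.** A design effect belongs to a particular session size. The 1.7 is correct for 8 per session and for no other size at this correlation, so 825 is the right inflated number only if sessions average 8. Sixty such sessions do not produce 825 people. If sessions are larger, so that 60 of them do produce 825, the 1.7 no longer applies and 825 is too few for the stated power.

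This matters because, with a correlation of 0.1, extra participants in a session add little information, and the number of sessions is the more important design quantity. A team that treats 60 as the operational target and recruits at the stated rate would stop 345 short of the stated minimum (825 - 480). A team that reaches 825 or 1,080 in 60 sessions would still fall below the stated 95% for one of the two primary quitting outcomes.

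**Working it through.** **Inputs.** From Section 17: rates 0.20 and 0.08, 95% power, 5% significance, 2:1 allocation, 8 per session, ICC 0.1, 825 participants, 60 sessions. From Section 16: 720 + 360 = 1,080. Sidedness is not stated; two-sided reproduces the plan's figure.

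**1. Reproduce 485.** Pooled two-proportion formula, with average rate p̄ = (0.08 + 2 × 0.20)/3 = 0.16:

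n(control) = [1.960 × √(0.16 × 0.84 × 1.5) + 1.645 × √(0.08 × 0.92 + 0.20 × 0.80/2)]² / 0.12² = (0.880 + 0.645)² / 0.0144 = 161.4

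This gives 162 control and 323 experimental, 485 in all. It agrees with the plan.

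**2. Reproduce 825.** Design effect = 1 + (8 - 1) × 0.1 = 1.7, and 485 × 1.7 = 824.5, so 825. It agrees.

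**3. Session count.** 825/8 = 103.1, so 104 sessions; 60 × 8 = 480. The 60 does not reproduce. It lies close to 485/8 = 60.6, which suggests that the session count was taken before inflation. The document does not say so, and the conflict does not depend on it.

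**4. Keep 60 sessions and let session size grow.**
- 825/60 = 13.75 per session; design effect 1 + 12.75 × 0.1 = 2.275; required number 485 × 2.275 = 1,103.4, so 1,104, which exceeds 825.
- 1,080/60 = 18 per session; design effect 2.7; required number 485 × 2.7 = 1,309.5, so 1,310, which exceeds 1,080.

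**5. Power with 60 sessions.** In each arm, effective n = participants / [1 + (m - 1) × 0.1], where m is that arm's mean session size. Power = Φ[(0.12 - 1.960 × s₀)/s₁], where s₀ is the standard error from the pooled rate and s₁ the standard error from the separate rates. The unpooled test replaces s₀ by s₁. Participants are 2:1 throughout. Sessions are split either 40:20 (equal session sizes) or 30:30 (experimental sessions twice as large).

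| Participants | Sessions | m (exp / control) | Design effect | Effective n | Power, pooled | Power, unpooled |
|---|---|---|---|---|---|---|
| 480 | 40:20 | 8 / 8 | 1.7 / 1.7 | 188 / 94 | 77% | 84% |
| 480 | 30:30 | 10.7 / 5.3 | 1.97 / 1.43 | 163 / 112 | 80% | 84% |
| 825 | 40:20 | 13.75 / 13.75 | 2.275 / 2.275 | 242 / 121 | 87% | 92% |
| 825 | 30:30 | 18.3 / 9.2 | 2.73 / 1.82 | 201 / 151 | 90% | 92% |
| 1,080 | 40:20 | 18 / 18 | 2.7 / 2.7 | 267 / 133 | 90% | 94% |
| 1,080 | 30:30 | 24 / 12 | 3.3 / 2.1 | 218 / 171 | 92.5% | 94% |

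Worked case, last row: p̄ = (218.2 × 0.20 + 171.4 × 0.08)/389.6 = 0.147; s₀ = 0.0362; s₁ = 0.0341; (0.12 - 1.960 × 0.0362)/0.0341 = 1.44; Φ(1.44) = 0.925.

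**6. What 95% would take.** Solving the same pooled formula with 60 sessions gives about 1,535 participants (30:30) or 2,265 (40:20); the unpooled form gives roughly 1,220 to 1,260. At 825 participants, about 92 sessions (equal split) or 103 (2:1) are needed with the pooled form, and about 76 to 78 with the unpooled form. At 1,080, the counts are about 73 or 82 pooled, and about 64 or 65 unpooled. Every version exceeds what the plan states.

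**7. The other primary outcome.** Taking 40% against 20% from Section 16, pooled power with 60 sessions is about 98% at 825 and 99% at 1,080.

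**Side note on 421.** Section 17 says "the required sample size for detecting a significant difference in the proportion of using any SC service is 421", by a similar calculation, without giving the rates. With 40% against 20% and the inputs that give 485, the result is 300.6 × 1.7 = 511. Two-sided 90% power gives 245.6 × 1.7 = 418, and one-sided 5% with 95% power gives 248.4 × 1.7 = 422. All are below 825, so the trial size is unaffected.

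**The case against.** The fairest defence is that 825 is called a minimum, that 8 per session is described as conservative, and that the working target is 1,080. On that reading nobody expected 60 sessions of 8, and 480 participants is the least likely outcome. At 1,080 the shortfall is 1 to 5 percentage points depending on test and split, and the service-use outcome is amply powered. This stands as to size: the trial is not badly underpowered at its target. It does not remove the contradiction. A low session size is conservative for the recruitment forecast but not for the design effect, which rises as sessions grow. If the word also covers the ICC, the plan gives no smaller value to use.

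A second objection is that the planned analysis uses generalized estimating equations rather than a pooled z-test, so pooled requirements may overstate the gap. That is fair, and both forms are shown. The pooled form is the one that yields the plan's 485, and the unpooled form also stays below 95%.

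Third, Section 12 allocates sessions within hotspots and puts two same-day sessions at a hotspot in the same group, so some allocation units are pairs. Neither feature is modelled here, and they may act in opposite directions. The session counts in step 6 are therefore approximate.

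**Conclusion.** The point holds. Three figures in one section are incompatible, and nothing elsewhere in the document reconciles them. With 60 sessions and the plan's ICC, the stated 95% power for quit attempts is not reached at 480, 825 or 1,080 participants, so the closing claim of sufficiency is unsupported at that power. At the target with a 30:30 split, the shortfall is about 2.5 points by the formula that reproduces 485, and about 1 point unpooled.

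The 30:30 split is an inference. The reason given in Section 8 for the 2:1 participant ratio, and the equal numbers advised per arm in Section 16, both fit roughly equal sessions better than 40:20. The conclusion is the same under either split.

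The power figures assume a two-sided 5% test, equal session sizes within arm and no dropout. Variable session sizes or dropout would lower power. At 8 per session, for example, an assumed coefficient of variation of 0.5 in session size raises the design effect from 1.7 to 1.9. This should be corrected, but it does not invalidate the design.

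**What to change.** Reconcile the session size, participant total and session total in Section 17, and state how sessions are divided between arms. There are two ways to do it:

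- **Keep 60 sessions.** Restate the expected participants per session and the matching design effect: 2.275 at 13.75 per session, or 2.7 at 18. If sessions are split equally, give it by arm (3.3 and 2.1 at the 1,080 target). Then state the resulting power and name the test: 87-90% pooled or about 92% unpooled at 825; 90-92.5% pooled or about 94% unpooled at 1,080. This costs only wording and a slightly lower stated power. It needs no extra participants or sessions.
- **Keep 8 per session and 825 participants.** State 104 sessions. This preserves the 95% but requires 44 more sessions than the 60 now written.

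The first is the inexpensive route. In the same edit, give the rates, power and sidedness behind 421, or restate it; this does not change the size of the trial.

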The primary process outcomes are the number and proportion of smokers that can be recruited for further follow-up, including those who will not participate in the RCT but agree to enroll in the SC clinics. We hypothesize that the promotion sessions providing NRT sampling will recruit more smokers, and greater proportion of recruited smokers among those who will be approached than those sessions without NRT sample. Other secondary process outcomes include (1) total number of smokers who can be approached in outdoor urban places; and (2) number of smokers who accept the brief SC advice. All these indicators will be documented by the SCAs in the promotion sessions.

Phase 3: Quitting outcomes

The evaluation aims to assess the effectiveness of NRT sampling on using the SC services and quit attempts, by comparing the outcomes between the experimental group and the control group. The two primary outcomes include (1) the proportion of smokers who enroll in any SC service in Hong Kong within 1 month of the recruitment; and (2) the proportion of smokers who report quit attempts at 1 month follow-up. Secondary outcomes include (1) the above outcomes at 3-month follow-up; (2) self-reported use of NRT in past month at 1- and 3-month follow-up; (3) self-reported tobacco abstinence in past 7 days and 4 weeks at 3- and 6-month follow-up; (4) biochemically validated abstinence at 6-month follow-up; (5) perceived importance, difficulty and confidence to quit smoking (score 0-10); (6) progression towards smoking cessation as measured by Incremental Behavior Change toward Smoking cessation (IBC-S) [1]. All self-reported outcomes will be assessed either

by telephone or WhatsApp by allocation-blinded interviewers at 1, 3 and 6 months after the recruitment. Self-reported quitters (no use of tobacco products for 7 days) will be invited for examination of exhaled carbon monoxide with a Smokerlyzer, and to undertake a saliva cotinine test. Validated quitters were defined by exhaled CO < 4 ppm and salivary cotinine < 10 ng/ml, which have been confirmed as the cut-off in clinical trials to verify smoking abstinence [2,3]. A HK\$50 shopping voucher will be given for each participation of follow-up and biochemical validation. We have much experience for the above and have reported these in many papers [4-8].

6. Estimated duration and commencement date

Proposed starting date: 1 July 2018

Proposed study completion date: 30 June 2020

Expected final report date: 30 June 2020

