In the experimental sessions, the SCAs will approach and distribute souvenirs (e.g. a pen) or leaflets to the smokers at outdoor smoking hotspots for 3-4 hours. The souvenirs and leaflets will have SC messages, quitline number and other SC services. If a smoker is willing to accept them and talk to the SCAs, the SCAs will advise the smoker to quit using the AWARD protocol. The AWARD protocol includes (1) Ask the smoking history, (2) Warn about the high risk (i.e., half of the smokers will die of smoking-related diseases), (3) Advise to quit, (4) Refer to the SC clinics of TWGHs and (5) Repeat the above advice (Do-it-again) [4]. Our previous studies have shown that the AWARD protocol is a feasible and appropriate tool used by non-healthcare professionals to promote smoking cessation [4-6]. If the smoker is interested in using the SC services, the SCAs will introduce NRT to the smoker and conduct a preliminary assessment of his/her eligibility for enrolling in the "NRT sampling" programme. The SCAs will invite him/her to go to the smoking cessation

truck nearby to receive counselling by an onsite nurse. If the smoker is not eligible, he/she can still enroll in the cessation service provided by the SC clinics.

11. Intervention: NRT sampling and medication counselling

In the experimental sessions, an onsite nurse will assess whether each participant is fit for using NRT with further assessment on his/her current physical status, medication and blood pressure. If the participant is willing to use NRT to quit smoking and pass the nurse's assessment, he/she will be prescribed the NRT sample, regardless of whether they use NRT for smoking reduction and when the quit day is. The nurse will help the participant decide which type of NRT product (gum: 2mg, patch: 14mg or 21mg) that he/she can use and advise him/her on how to use the NRT based on his/her smoking habit and daily cigarette consumption. In addition, the nurse will deliver medication counselling which addresses five main components: (1) the benefits for using NRT in quitting, (2) withdrawal symptoms due to smoking cessation, (3) side effects of NRT, (4) instructions for using NRT, and (5) making appointments for TWGHs SC clinics. Afterwards, the participant will receive 1-week free NRT and an instruction card about the use of NRT.

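### The Poisson model for the recruitment outcomes fixes the variance and ignores session, day and hotspot, so its intervals and tests can be too narrow or too wide

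*Combined protocol and SAP*

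**What the plan says.** Section 5 (Phase 2) makes the number and proportion of smokers recruited for follow-up the primary process outcomes, "including those who will not participate in the RCT but agree to enroll in the SC clinics". It hypothesises that "promotion sessions providing NRT sampling will recruit more smokers, and greater proportion of recruited smokers among those who will be approached" than sessions without a sample. It adds: "All these indicators will be documented by the SCAs in the promotion sessions".

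Section 10 shows how a smoker can be recruited outside the trial: "If the smoker is not eligible, he/she can still enroll in the cessation service provided by the SC clinics".

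On design, Section 12 states "We will use cluster randomization based on promotion session as the cluster unit", and Section 8 states that "the promotion sessions of one hotspot will be randomly allocated to either group". Section 12 also puts two sessions held at one hotspot on one day into the same arm, with two more to follow on another day.

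On analysis, Section 18 states that "the number of smokers who accept the brief advice or consent for the trial in each promotion session will be the outcome variables" of a "Poisson regression model, with group allocation as the predictor, and total number of approached smokers in that promotion session as the offset variable". It names generalized estimating equations and linear mixed models for the quitting outcomes and the secondary outcomes listed with them, not for recruitment. An ICC (0.1, design effect 1.7) appears only in Section 17, for the quit-attempt sample size.

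**The concern.** A Poisson model with only group and an offset takes its standard error from the total counts. The variation seen between sessions does not enter. Three features of the design make that variance doubtful:

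- **Session and day.** Recruitment can vary by staff, weather or time. If this variation is large enough, the reported interval is too narrow. Variation shared within a day is worse, because both sessions of that day are in one arm.
- **Hotspot.** If each hotspot receives both arms, differences between hotspots cancel from the comparison, and a model that ignores hotspot can give an interval that is too wide.
- **Bounded counts.** The number recruited cannot exceed the number approached. With little clustering the true variance is below the Poisson value, and the interval is too wide.

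A second gap is that the modelled counts do not match the declared outcome. At stake are the interval for the primary process outcome and the validity of its test when the difference is small. Acceptance of advice is modelled in the same way, and no large effect is assumed for it.

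**Working it through.** **Inputs from the protocol.** Section 16: 2,400 smokers given advice, 1,200 per group; 720 (60%) and 360 (30%) consent. Targets 3 and 6 take these percentages of those approached, so 2,400 is used here as the number approached. Section 17: 60 sessions, or 8 participants per session, which implies 825/8 ≈ 103 sessions, or 1,080/8 = 135 at the Section 16 targets. Approached per session is therefore m = 40, 23.3 or 17.8.

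**Assumptions.** The ICC for recruitment is not given; 0 to 0.1 is used, the upper value borrowed from quit attempts. Sessions are split equally between arms and the test is two-sided at 5%.

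**The plan's own clustering figure.** For 8% against 20%, 95% power and 2:1 allocation, the pooled normal formula gives 486 (stated: 485). The design effect is 1 + (8 − 1) × 0.1 = 1.7, and 1.7 × 485 = 824.5, i.e. 825. It reproduces, but concerns quit attempts only.

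**Model standard error at the planned counts.** √(1/720 + 1/360) = 0.0645. Neither the number of sessions nor their variation appears.

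**Independent sessions.** Variance relative to Poisson is φ = (1 − p)[1 + (m − 1)ICC], and type I error is 2Φ(−1.96/√φ). Example: p = 0.30, m = 40, ICC 0.1 gives φ = 0.7 × 4.9 = 3.43 and type I error 29.0%.

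| Type I error at p = 30 / 45 / 60% | ICC 0 | ICC 0.05 | ICC 0.1 |
|---|---|---|---|
| m = 40 | 1.9 / 0.8 / 0.2% | 17.3 / 12.4 / 7.1% | 29.0 / 23.3 / 16.2% |
| m = 23.3 | same | 10.7 / 6.9 / 3.3% | 19.2 / 14.1 / 8.5% |
| m = 17.8 | same | 8.4 / 5.1 / 2.2% | 15.2 / 10.6 / 5.8% |

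The model is exact when ICC = p/[(1 − p)(m − 1)]. At m = 40 that is 0.011, 0.021 and 0.038 for the three rates. Below it the test is conservative, above it anti-conservative.

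If only half of those approached accept advice (4,800 approached, 1,080 recruited, p = 22.5%), type I error at ICC 0.1 is 29–46% over 135 to 60 sessions. With 2,400 approached and p = 45% it is 11–23%.

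**Planned effect, m = 40.** True variance is φ₁/720 + φ₀/360. At ICC 0: 0.4/720 + 0.7/360 = 0.0025, SE 0.0500, or 0.77 of the model SE. At ICC 0.1: 1.96/720 + 3.43/360 = 0.01225, SE 0.1107, or 1.71 times the model SE.

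**Hotspots and days.** The simulation assumed 15 hotspots × 2 days × 2 sessions × 40 approached, one day per arm, ICC 0.1, 10,000 replicates per cell.

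| Where the variance lies | Plain Poisson, p = 30 / 45 / 60% | Session-level quasi-Poisson, no hotspot term |
|---|---|---|
| Independent sessions | 28.7 / 22.6 / 16.5% | 4.9 / 4.7 / 5.2% |
| Half at hotspot level | 16.7 / 11.6 / 6.7% | 1.3 / 1.3 / 1.0% |
| 80% at hotspot level | 7.0 / 4.3 / 1.7% | 0.2 / 0.2 / 0.2% |
| Half shared within a day | 36.8 / 31.5 / 23.8% | 9.8 / 10.2 / 9.7% |

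If hotspot-days are allocated without ensuring both arms at each hotspot, the two hotspot-level rows for plain Poisson become 23–40%.

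Quasi-Poisson on hotspot-day totals with hotspot terms and a t reference on 30 − 15 − 1 = 14 df rejected 3.8–5.2% over all structures and ICCs of 0.01, 0.05 and 0.1. CR2 standard errors on hotspot-day with t(14) gave 4.5–5.4%. An uncorrected robust SE gave 18.9–20.8%.

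**Interval for the planned ratio of 2.0.** Plain Poisson: 2·exp(±1.96 × 0.0645) = 1.76–2.27. Using the simulated SD and t(14) = 2.145: 1.66–2.41 (80% hotspot, SD 0.0860) to 1.51–2.66 (half day-shared, SD 0.1321). Power stays above 99.9%.

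**Smallest significant ratio with 30% in control.** Plain Poisson about 1.15. Allowing for clustering at ICC 0.1: 1.21–1.28 with independent sessions (normal reference), 1.18–1.37 across the layout above (t(14)).

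**Outcome definition.** Section 5 counts everyone recruited for follow-up, including clinic enrolees outside the RCT. Section 18 models acceptance of advice and trial consent. Consent leaves those enrolees out. Acceptance would normally include them, together with many who were not recruited. Neither isolates the declared outcome.

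**The case against.** The model already uses one count per session, so the analysis unit is the stated randomised unit, and the plan is silent on standard errors rather than ruling out robust ones. That is fair as description, but session counts alone do not estimate between-session variance. Followed as written, the model returns 0.0645 whatever the data show.

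The size rests on inputs the plan does not give: the ICC, the hotspot layout and the number approached. This stands, so the error rates are illustrations. The recruitment rate matters too. Section 7 reports 77.6% of approached smokers accepting a sample and 81.3% of invited smokers participating; at m = 40 and ICC 0.1 these give about 6% and 4%. Section 5's outcome for advice acceptance is not evaluated at all, since 2,400 serves as both advised and approached. Against that, the earlier hotspot project in Section 7 recruited 210 of 3,096 (6.8%), which at m = 40 gives 8.5% at ICC 0.01 and 24% at ICC 0.05. Not knowing the variance is a reason to estimate it.

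Part of the widening in the corrected intervals comes from t(14) in place of z (2.145/1.96 = 1.09). That is true, and it is a small part of the larger differences.

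A session-level overdispersed variance could be enough. It is, if sessions are independent; it is conservative with hotspot variance and too liberal with shared days. Finally, this is a process outcome and the planned effect would survive. That limits the grade but does not remove the point.

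**Conclusion.** The concern holds and should be fixed. The omission is certain from the text: no part of the protocol adds a variance allowance to the recruitment model. The direction and size of the resulting error are not determined, because they depend on an unstated ICC, on session size and on whether variation lies between sessions, days or hotspots. With independent sessions over the assumed 60 to 135, recruitment of 30–60% and a two-sided 5% test, type I error runs from 0.2–1.9% at ICC 0 to 6–29% at ICC 0.1. The planned 60% against 30% stays significant in every structure examined at ICC 0.1, but its interval could be clearly wider than the one reported. A modest difference, with a ratio of roughly 1.15 to 1.37, could be declared significant when it should not be. The primary quitting outcomes use a different model and are untouched. Separately, the outcome that Section 5 declares primary for this phase is not among the counts Section 18 analyses.

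**What to change.** In Section 18:

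1. Keep the log of the number approached as offset and add hotspot as a stratum.
2. Estimate the variance at the unit actually allocated, which is the hotspot-day where two sessions share an allocation. Either quasi-Poisson on hotspot-day totals with hotspot terms and a t reference on the residual degrees of freedom, or cluster-robust standard errors on hotspot-day with a bias-reduced (CR2-type) correction, would do. An uncorrected robust SE is too small when a hotspot has only two days. Session-level quasi-Poisson or negative binomial without hotspot and day is not enough if days share variation: adding hotspot terms alone still gave 11.6–12.2% in the half day-shared case.
3. Add, as an outcome, all smokers recruited for follow-up as Section 5 defines them, including clinic enrolees outside the RCT.

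The cost is analysis wording; Section 5 already has these indicators recorded in the sessions. Intervals may widen: at ICC 0.1 and the planned rates the SE is about 1.3–1.7 times the plain Poisson SE with independent sessions, and 1.3–2.0 times in the assumed layout. A hotspot that ends up with only one arm would contribute nothing to the stratified comparison.
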